Profiling the vaginal and seminal microbiome and human virome in a smaller cohort of patients going through their first IVF cycle is an exploratory portion of this study. Existing studies are limited and conflicting regarding influence of the microbiome on IVF cycle outcomes.¹¹⁻¹³ This would be the first study to evaluate alterations in the reproductive tract microbiome across the IVF cycle in response to medications and supraphysiologic hormone levels, and the first to evaluate the human virome in this patient population.^{6,7} We would examine differences within and between groups and assess for the potential impact and association clinical outcomes of those patients exposed to prophylactic azithromycin, and those who are not. Optimizing the vaginal microbiome could serve as a potential target for therapy to help increase IVF success rates in the future with the goal of a full term, live birth.

C Study Objectives

C1 Primary Aim

Specific Aim 1: Determine the effect of withholding prophylactic antibiotic administration on clinical pregnancy rate (defined as a gestational sac, with fetal pole and cardiac activity, on ultrasound).

We *hypothesize* that withholding prophylactic antibiotics before embryo transfer will be non-inferior (absolute difference $\leq 15\%$) to routine prophylaxis in terms of clinical pregnancy rates.

C2 Secondary Aim

Specific Aim 2: Evaluate the impact of prophylactic antibiotic administration on miscarriage rate (pregnancy loss per clinical pregnancy) before 20 weeks.

Our *working hypothesis* is that miscarriage rates will be equivalent between the two groups.

Specific Aim 3: Determine the effect of no prophylactic antibiotic administration on embryo development.

We *hypothesize* that embryo development, as evaluated by fertilization rate (number of two-pronuclei embryos per mature oocyte), blastocyst conversion rate (number of day 5 embryos from two-pronuclei embryos), and blastocyst utilization rate (number of day 5 embryos transferred or frozen per two-pronuclei embryos) will be equivalent between the two groups.

Specific Aim 4: Determine the impact of prophylactic antibiotics or withholding prophylaxis on the vaginal and endometrial microbiome.

We *hypothesize* that azithromycin will impact the vaginal microbiome. Additionally, we expect to see changes across the IVF cycle that may be associated with cycle outcome endpoints.

Specific Aim 5: Evaluate the implications of the human virome on IVF outcomes.

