Azithromycin is routinely given to both partners (in male/female couples) or to the embryo recipient in same sex couples or gestational carriers when they start their IVF cycle medications and is our current standard of care.

3.b Treatment Regimen

1 gram oral azithromycin, once the day of IVF cycle start (when they start injectable gonadotropin medications) which is our current standard of care.

3.c Method for Assigning Subjects to Treatment Groups

Computer random number generator.

3.d Preparation and Administration of Study Drug

Azithromycine will be prepared and dispensed by the patients preferred pharmacy as is standard practice if they are randomized to the antibiotic prophylaxis group.

3.e Subject Compliance Monitoring

Patients will give verbal confirmation of compliance.

3.f Blinding of Study Drug

Patients will not be blinded to which group they're in. A placebo control will not be used.

3.g Receiving, Storage, Dispensing and Return

Azithromycin will be prepared and dispensed by the patients preferred pharmacy as is standard practice if they are randomized to the antibiotic prophylaxis group.

E Study Procedures

E1 Screening for Eligibility

Couples will be screened for eligibility by their primary physician, the primary investigator, [name] or the Research Project Coordinator. If they meet the inclusion and exclusion criteria they will be offered enrollment.

E2 Schedule of Measurements

Outcomes measures are routinely tracked by our clinical to report to the Society of Assisted Reproductive Technology (SART). Patients who participate in the study will not be required to make any additional visits beyond consent.

E3 Visit 1

Outcome measures for specific aim 3 will be tracked from the patients initial oocyte retrieval and embryo transfer visit. The lab routinely tracks this data and no additional query or visits will be required in term of embryo development data.

E4 Visit 2 etc.

Specific Aim 1 will be addressed and tracked when patients come in for their viability ultrasound at 6-7 weeks gestation which is routine practice in our clinic. Clinical pregnancy is defined as a gestational sac, with fetal pole and cardiac activity, on

ultrasound. No additional visits will be required. Patients will continue to be tracked once they are released from our practice to their primary OBGYN to track miscarriage rate (spontaneous loss prior to 20 weeks) and subsequent live birth outcomes.

Schedule of Visits for Microbiome/Virome Study:

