Severe adverse events: pelvic infection (endometritis, cervicitis or pelvic inflammatory disease) as diagnosed by cervical culture and physical exam, spontaneous miscarriage (pregnancy loss prior to 20 weeks gestation) or increased contamination rates in the lab which is routinely monitored for by our embryologists.

Non-severe adverse events include adverse effects of antibiotic administration including yeast vaginitis, abdominal pain, diarrhea, nausea and vomiting.

5.d Classification of Events

Reportable severe events include development of pelvic infection following embryo transfer, a significant increase in spontaneous miscarriage rates or a note in increased contamination rates in the lab. Risks of pelvic infection in this low risk population following embryo transfer approaches zero and we do not anticipate this occurring. We anticipate miscarriage rates to be equivalent or improved in the non-prophylaxis group but will be closely tracked for any increase in incidence. The lab uses gentamicin routinely in embryo culture media to decrease contamination rates and will continue to be closely monitored as is standard for quality control measures in our lab for any increase in contamination rates.

Reportable non-severe adverse events include yeast vaginitis, nausea and vomiting or other adverse reactions from antibiotic prophylaxis which the patients will report to their nurses.

5.e Data Collection Procedures for Adverse Events

In addition to principle investigator review of adverse events, a data and safety monitoring board (DSMB) will be established. This will include [name], [name], [name] and [name] and [name], MSCI. The designated group will meet once enrollment reaches 50% and then every 6 months thereafter. Adverse events will be noted in the patients chart and in the redcap database for complete capture and tracking. Data will be analyzed if a noted increase in severe adverse events is noted or otherwise once enrollment reaches 50% and then every 6 months thereafter when the DSMB meets.

5.f Reporting Procedures

Patients will be instructed to report any adverse symptoms to their respective nurse or doctor. These events will be immediately reported to the PI or research project coordinator.

5.g Adverse Event Reporting Period

Until study completion.

-

F Statistical Plan

F1 Sample Size Determination and Power

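### Aim 2 compares miscarriage only among clinical pregnancies, a subset fixed after randomisation by the primary outcome; one definition and a per-randomised-couple comparison should be added

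*Combined protocol and SAP*

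**What the plan says.** C2 (Specific Aim 2) gives the only miscarriage rate with a stated denominator: "miscarriage rate (pregnancy loss per clinical pregnancy) before 20 weeks". The working hypothesis is that "miscarriage rates will be equivalent between the two groups", and no equivalence margin is given. C1 fixes the denominator: "clinical pregnancy rate (defined as a gestational sac, with fetal pole and cardiac activity, on ultrasound". E4 places its ascertainment at the "viability ultrasound at 6-7 weeks gestation which is routine practice in our clinic".

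E4 then says that patients are followed after handover to their own obstetrician to "track miscarriage rate (spontaneous loss prior to 20 weeks) and subsequent live birth outcomes". E5 5.c lists "spontaneous miscarriage (pregnancy loss prior to 20 weeks gestation" among severe adverse events, and 5.d makes reportable "a significant increase in spontaneous miscarriage rates or a note in increased contamination rates in the lab", without a denominator. None of these places says whether a loss before the scan, or a sac without cardiac activity, counts.

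F4 names miscarriage as a secondary analysis. It announces intention-to-treat and per-protocol analyses in general, but gives no analysis set or denominator for miscarriage. Live birth (D1, F4) is planned, also without a stated denominator.

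**The concern.** Randomisation makes the two groups of couples comparable. It does not make the two groups of clinical pregnancies comparable, because reaching a clinical pregnancy may itself depend on the arm. If one arm loses more pregnancies before the scan, those that remain may be fewer and sturdier, and that arm can show a lower later loss rate for this reason alone. The trial cannot assume this away: whether withholding antibiotics changes the clinical pregnancy rate is its primary question.

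There is also an open point of definition. If only losses after the scan count, the rate is coherent but says nothing about earlier loss. If losses before the scan count too, women enter the numerator who are not in the denominator. Miscarriage is also a safety outcome (E5 5.c and 5.d), and F2 ties continuation to the absence of a trend toward severe adverse outcomes. The monitoring board and the final analysis could therefore use different quantities under one name.

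**Working it through.** **The plan's own figure.** Inputs from F1: 41% in both arms, margin 15 points, one-sided alpha 0.025, power 80%, dropout 5%.

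n per arm = (1.960 + 0.842)² × 2 × 0.41 × 0.59 / 0.15² = 7.85 × 0.4838 / 0.0225 = 168.8, so 169. With dropout, 169 / 0.95 = 177.9, so 178 per arm and 356 in total. The stated size reproduces exactly. It concerns the primary endpoint only; the documents give no figure for miscarriage.

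**Size of the Aim 2 subset.** 0.41 × 178 = 73 clinical pregnancies per arm, or 0.41 × 169 = 69 after dropout. With 69 per arm and an assumed miscarriage rate r, the 95% half-width for the difference is 1.96 × √(2r(1 − r)/69): 10.0 points at r = 10% and 14.4 points at r = 25%.

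**Can the direction differ?** The documents give no loss rates, so the loss counts here are assumptions. Take 178 couples and 80 pregnancies per arm.
- Antibiotic: 7 lost before the scan, 73 clinical pregnancies, 11 lost later.
- No antibiotic: 13 lost before the scan, 67 clinical pregnancies, 9 lost later.

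| Measure | Antibiotic | No antibiotic | Favours |
|---|---|---|---|
| Losses after scan / clinical pregnancies | 11/73 = 15.1% | 9/67 = 13.4% | withholding |
| All losses / clinical pregnancies | 18/73 = 24.7% | 22/67 = 32.8% | antibiotic |
| All losses / couples | 18/178 = 10.1% | 22/178 = 12.4% | antibiotic |
| Losses after scan / couples | 11/178 = 6.2% | 9/178 = 5.1% | withholding |
| Clinical pregnancies / couples | 73/178 = 41.0% | 67/178 = 37.6% | antibiotic |
| Pregnancies remaining / couples | 62/178 = 34.8% | 58/178 = 32.6% | antibiotic |

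The reason is an identity: all losses per couple = losses before the scan per couple + (clinical pregnancy rate × later loss per clinical pregnancy). This gives 3.9% + 6.2% = 10.1% against 7.3% + 5.1% = 12.4%. The C2 rate sees only the last factor. The fourth row shows that changing the denominator alone is not enough: losses before the scan must be counted, or clinical pregnancy and live birth must stand beside the rate.

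In this example the primary endpoint still meets its margin. The difference is −3.4 points, with standard error √(0.410 × 0.590/178 + 0.376 × 0.624/178) = 5.17 points, so the lower 95% limit is −3.4 − 1.96 × 5.17 = −13.5, inside −15.

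**Sampling error in the example.** The first row differs by 1.6 points (before rounding), with a 95% half-width of 11.6. All losses per couple differ by 2.2 points, with a half-width of 6.6.

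**What the ambiguity could do to the level.** If a share e of pregnancies is lost before the scan and these are counted over clinical pregnancies, the rate becomes r + e/(1 − e). With r = 15% (assumed), e = 5% gives 20.3% and e = 20% gives 40.0%.

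**The case against.** A reader might infer that numerator and denominator demonstrably do not match. The documents do not support this. The C2 wording reads naturally as losses among clinical pregnancies, which is a proper proportion. E4 places miscarriage follow-up after the viability scan, and E5 5.c defines an adverse event rather than the Aim 2 endpoint. What stands is an ambiguity.

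A reader might also infer that the plan hides early loss. For the trial as a whole it does not: a pregnancy lost before the scan is a failure on the primary endpoint and lowers live birth. In the example, 41.0% against 37.6% and 34.8% against 32.6% both show it. On the primary endpoint, however, it cannot be told apart from never conceiving.

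A third inference would be that a reversal is likely. The counts are assumed and the gap is within noise; two more late losses without antibiotics (11/67 = 16.4%) would remove it. Nor do the documents present early loss as an expected effect of withholding: B1 cites a retrospective series without a significant difference in clinical miscarriage, and E5 5.d anticipates rates equal or better without prophylaxis.

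Finally, loss per couple has its own distortion, because it falls when fewer women conceive. With assumed counts of 18 losses from 80 pregnancies against 15 from 60, it is 10.1% against 8.4% of 178 couples, although loss per pregnancy is 22.5% against 25%. This objection stands in full, and the fix must allow for it.

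**Conclusion.** The point holds on every reading of the definition. The only miscarriage rate that C2 specifies is conditional on the primary outcome, so the Aim 2 comparison is not a comparison of randomised groups, and its direction could differ from one that is. The possibility is arithmetical: no loss rate in the documents allows its likelihood to be sized, and the illustration rests on assumed counts. Whether losses before the scan count is unresolved in E4 and E5 5.c, but this is missing detail and not a proven contradiction. The matter touches a secondary endpoint and the reading of safety data; the primary analysis and the 356 couples are unaffected. It is a cheap improvement.

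**What to change.** - Use one definition of miscarriage in C2, E4 and E5 5.c, and state whether losses before the scan count.
- Keep loss per clinical pregnancy, limit its numerator to losses after documented cardiac activity, and label it a conditional, descriptive measure.
- For the arm comparison, report losses before 20 weeks per randomised couple, with losses before the scan shown separately where the clinic records them. Put clinical pregnancy and live birth per randomised couple beside it, and read the three together.
- State that the denominator is every couple allocated, including those without retrieval or transfer whom D2 2.f would leave out.

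The cost is wording in three places and one table. Loss per couple is less familiar to clinicians and falls when fewer women conceive. The sponsor must also confirm that early positive tests are captured: Table 2 lists only clinical pregnancy, miscarriage and live birth as cycle outcomes. If they are not captured, the table should say so, and the per-couple figure then covers losses after the scan only.

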partners. Patients may be hesitant to deviate from our previous standard of care. On the other hand, patients may want to avoid additional medication and may not take the antibiotic regardless to which arm they are randomized. We would mitigate this risk by a thorough informed consent and expressing our goal is to improve our current IVF protocols and that the best approach is not known while emphasizing the importance of compliance. Reportable severe events include development of pelvic infection following embryo transfer, a significant increase in spontaneous miscarriage rates or a note in increased contamination rates in the lab. Risks of pelvic infection in this low risk population following embryo transfer is remarkably rare as stated above and we do not anticipate this occurring. We anticipate miscarriage rates to be equivalent or improved in the non-prophylaxis group. The lab uses genatmicin routinely in embryo culture media to decrease contamination rates and will continue to be closely monitored for any increase in contamination rates. Reportable non-severe adverse events include yeast vaginitis, nausea and vomiting or other adverse reactions from antibiotic prophylaxis.

Obtaining a mid-vaginal swab poses little to no risk to the patient. The patient may experience some slight discomfort from one additional speculum exam at the time of baseline testing. The embryo transfer catheter tip will be sequenced for comparison to the vaginal swab following embryo transfer and will require no additional invasive testing or exams.

2.f Early Withdrawal of Subjects

While loss to follow up is extremely rare in this circumstance, some patients who are enrolled and randomized may not make it to egg retrieval or may not get an embryo transfer due to either a poor response to medications or poor embryo quality. We will account for these patients in our 5% drop out estimation and they will not be included in analysis.

2.g When and How to Withdraw Subjects

Patients can withdraw from the study at any time if they choose to do so. Their care will not be impacted by their participation or lack thereof.

2.h Data Collection and Follow-up for Withdrawn Subjects

Subjects who withdraw will not be included in the final data analysis.

D3 Study Drug –

3.a Description

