Intention-to-treat and per protocol analyses will be performed. Chi-squared and Fisher's exact tests will be used to compare categorical variables as appropriate. Kolmogorov-Smirnov test will be initially used to assess the distribution pattern of continuous variables. Normally distributed variables will be analyzed via Student's t-test. Non-normally distributed continuous variables will be analyzed with the Mann-Whitney U test. The primary analysis is based on difference in clinical pregnancy rate between the two groups. The sample size estimation for the study is based on this comparison with a non-inferiority approach as described above with an absolute difference of 15% or less to be considered non-inferior. Secondary analyses will include spontaneous miscarriage rate and embryo development. A subsequent interval analysis will assess live birth rate. Pearson's correlation coefficients will be used to quantify the association

between the two groups and embryo development. $P < 0.05$ will be considered statistically significant.

Each microbiota sample will have the taxon indicated as relative abundance. To assess the diversity across an IVF cycle, after log transformation, linear mixed regression will be applied. Wilcoxon rank sum will be used to measure for difference in richness and diversity with clinical outcomes of clinical pregnancy rate, miscarriage rate and embryo outcomes.

IBM® SPSS® statistics version 23 will be used for all analyses.

F5 Missing Outcome Data

All outcome data is required to be tracked by SART and no additional query will be required. We do not anticipate any issues with missing outcome data.

G Data Handling and Record Keeping

G1 Confidentiality and Security

Our practice is required to track patient demographic data and cycle outcome measures to report to the Society for Assisted Reproductive Technology (SART). Data is currently recorded and tracked through Research Electronic Data Capture (REDCap). REDCap is a secure web-based application designed to support data capture for research studies, providing 1) an intuitive interface for validated data entry; 2) audit trails for tracking data manipulation and export procedures; 3) automated export procedures for seamless data downloads to common statistical packages; and 4) procedures for importing data from external sources.¹⁸ Enrolled patients will be exported and tracked in a separate REDCap data set from our existing dataset.

G2 Records Retention

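### Aims 2 and 3 hypothesise equivalence, but F4 gives them only tests of difference, with no margin or confidence-interval rule, so a non-significant result cannot support those hypotheses

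*Combined protocol and SAP*

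**What the plan says.** Section C2 (Secondary Aim) sets a hypothesis for each aim:

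- **Aim 2:** the working hypothesis "is that miscarriage rates will be equivalent between the two groups". The rate is defined per clinical pregnancy, with losses counted before 20 weeks.
- **Aim 3:** three embryo-development rates are expected to match, ending with day 5 embryos "transferred or frozen per two-pronuclei embryos) will be equivalent between the two groups".

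F4 (Statistical Methods) describes the analysis:

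- Chi-squared and Fisher's "exact tests will be used to compare categorical variables as appropriate". Continuous variables go to Student's t-test if normally distributed and to Mann-Whitney if not.
- Pearson's "correlation coefficients will be used to quantify the association" between group and embryo development.
- Significance is P below 0.05.
- "Secondary analyses will include spontaneous miscarriage rate and embryo development". F4 does not say how equivalence would be judged for them.

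The one margin in the plan is in C1, F1 and F4. F4 puts it as "an absolute difference of 15% or less to be considered non-inferior". In all three places it concerns clinical pregnancy.

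**The concern.** A test of difference asks whether the data contradict equality. Failing to contradict equality does not show that the arms are close, because a small or noisy comparison fails in the same way. To support equivalence, a plan needs a margin and a rule that the confidence interval must lie inside it. The authors supplied a margin for the one-sided non-inferiority question in Aim 1, but none for Aims 2 and 3, where equivalence is a two-sided claim.

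The Pearson correlation does not fill the gap. Correlating a rate with a two-level arm variable gives a unitless coefficient, not a difference in rate units. It applies to embryo development only, so miscarriage has just the categorical test.

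The risk is that a non-significant miscarriage comparison is later written up as equivalent when the data are compatible with a material increase. E5 5.c lists miscarriage among the severe adverse events. The DSMB review in E5 and F2 concerns safety and continuation, and sets no rule for the final Aim 2 conclusion.

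**Working it through.** **1. Reproduce the plan's own figure.** F1 gives a 41% clinical pregnancy rate, a 15-point margin, one-sided alpha 0.025, 80% power and 5% dropout.

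n per arm = (1.960 + 0.842)² x 2 x 0.41 x 0.59 / 0.15² = 168.8, so 169.
169 / 0.95 = 177.9, so 178 per arm and 356 in total. This matches F1. It sizes clinical pregnancy only.

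**2. Denominator for Aim 2.** Miscarriage is counted per clinical pregnancy: 0.41 x 169 = 69 per arm, or 0.41 x 178 = 73 if every randomised couple counts.

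**3. Assumption.** The documents give no miscarriage rate. I use q = 10%, 15% and 20%.

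**4. Precision and sensitivity with 69 pregnancies per arm (normal approximation).**

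- SE with equal rates = sqrt(2q(1 - q)/69). The 95% half-width is 1.960 x SE.
- Chance that a true rise from q to q + 10 points is non-significant at two-sided 0.05: about Phi(1.960 - 0.10/SE1), with SE1 = sqrt([q(1 - q) + (q + 0.10)(0.90 - q)]/69).
- Power to show equivalence when there is no true difference, using a 90% interval and margin M: max(0, 2 x Phi(M/SE - 1.645) - 1).

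| Assumed rate | SE (points) | 95% half-width (points) | True 10-point rise non-significant | Equivalence power, M = 10 | Equivalence power, M = 15 |
|---|---|---|---|---|---|
| 10% | 5.1 | 10.0 | 62% | 25% | 80% |
| 15% | 6.1 | 11.9 | 68% | 0% | 59% |
| 20% | 6.8 | 13.3 | 72% | 0% | 42% |

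Exact binomial calculation for the uncorrected chi-squared test gives 62.4%, 68.6% and 72.5% for the fourth column. With 73 pregnancies per arm the half-widths are 9.7, 11.6 and 13.0 points, and the non-significance rates are 60%, 67% and 71%.

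The 10- and 15-point margins are illustrations; the plan has no margin for miscarriage.

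**5. Aim 3.** With one value per couple and 169 couples per arm, the equivalence margin giving 80% power is (1.645 + 1.282) x sqrt(2/169) = 0.32 SD with a 90% interval, or (1.960 + 1.282) x sqrt(2/169) = 0.35 SD with a 95% interval. Fewer couples may contribute to the day 5 rates, which would widen these figures.

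**6. Pearson correlation.** With a two-level arm, t = r x sqrt(N - 2)/sqrt(1 - r²), where N is the total number of couples. This is the equal-variance t statistic. Where F4 uses the t-test, the correlation therefore returns the same P-value. Where F4 uses Mann-Whitney, it does not, but it still gives no difference in rate units.

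**The case against.** The strongest reply is that the aims themselves only evaluate an impact (Aim 2) or determine an effect (Aim 3). Equivalence appears in the expectation that follows, and Aim 2 labels it a working hypothesis. F4 calls these secondary analyses and announces no equivalence conclusion. That is fair, and it limits the weight of the point. It does not remove the mismatch, because a stated hypothesis still needs an analysis that could support it.

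A reader might infer more than the documents support:

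- **That the plan will declare equivalence when P is 0.05 or more.** No section says so, and none rules it out. The misreading is a risk left open.
- **That equivalence for miscarriage is out of reach.** This depends on the rate, margin and alpha. A 10-point margin looks hopeless or nearly so, but at 15 points with a 90% interval the power is 80%, 59% or 42%. I do not suggest that 15 points is clinically justified for miscarriage.
- **That the miscarriage hypothesis is worded two ways.** D2 2.e says "We anticipate miscarriage rates to be equivalent or improved in the non-prophylaxis group", and E5 5.d repeats it. Both are safety expectations, not a second hypothesis. At most this merits a wording note.
- **That Aim 3 is underpowered.** The figures do not show this; what is missing is the margin and interval rule.
- **That the 15-point margin can be borrowed.** It is a one-sided non-inferiority limit tied to clinical pregnancy.

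**Conclusion.** The concern holds for the secondary aims. C2 hypothesises equivalence for miscarriage and three embryo-development rates, and F4 provides only tests of difference, plus a correlation for embryo development that cannot express the size of a difference. This mismatch is visible in the text and depends on no assumed figure.

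The size for miscarriage rests on two inputs: about 69 pregnancies per arm, from F1, and an assumed rate of 10% to 20%. On these, the interval extends about 10 to 13 points on either side of the observed difference, and a true 10-point rise would usually go undetected. A lower miscarriage rate would narrow the interval. The Aim 1 conclusion and the sample size of 356 are untouched, so this is a correction that should be made rather than a threat to the trial.

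**What to change.** In F4, for Aims 2 and 3, replace the Pearson correlation and the bare P-value with the between-arm difference in rates and its 95% confidence interval. For embryo development, use one rate per couple. Then choose one of two routes:

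- **Estimation:** restate the Aim 2 and Aim 3 hypotheses in C2 as estimation of the difference, and say that P of 0.05 or more will not be read as equivalence.
- **Equivalence:** pre-specify a justified margin and alpha for each outcome, name the interval that decides, and claim equivalence only if that interval lies wholly within the margin.

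The choice should be made before outcome data are seen, because a margin set afterwards would carry little weight.

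The cost is plan wording and a few intervals, with no new data and no change to the sample size. The downside is that the miscarriage equivalence claim may have to be dropped, or made with a wide margin.

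### Sections 2.f and 2.h remove randomised couples from analysis without limiting this to the per-protocol set, so the intention-to-treat analysis promised in F4 cannot be done as written

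*Combined protocol and SAP*

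**What the plan says.** - **F4 (Statistical Methods):** "Intention-to-treat and per protocol analyses will be performed". Neither set is defined. F4 adds that "The primary analysis is based on difference in clinical pregnancy rate between the two groups", "with an absolute difference of 15% or less to be considered non-inferior", but gives no denominator for the rate and does not say which set decides.
- **D2 2.f (Early Withdrawal):** for couples enrolled and randomised who do not get to retrieval or transfer because of poor response or poor embryo quality, "We will account for these patients in our 5% drop out estimation and they will not be included in analysis".
- **D2 2.h:** "Subjects who withdraw will not be included in the final data analysis".
- **F1:** 178 per arm, from a 41% clinical pregnancy rate, a 15-point margin, 80% power, one-sided 0.025 and 5% dropout. It does not say whether 41% is per cycle started or per transfer.
- **Adherence:** 2.e foresees that some patients "may not take the antibiotic regardless to which arm they are randomized". Section 3.e plans only this: "Patients will give verbal confirmation of compliance".
- **Availability of outcomes:** E2 states that "Outcomes measures are routinely tracked by our clinical", and F5 expects no missing outcome data and gives no handling rule.

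**The concern.** An ITT analysis keeps every randomised couple in the arm assigned. Sections 2.f and 2.h take couples out for things that happen after randomisation and after the antibiotic is given at cycle start. Both rules speak of analysis without qualification, so they cover the ITT analysis too. Two analysts could each follow the document and report different primary sets.

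The excluded group could depend on the arm. Patients, providers and nurses know the allocation, so withdrawal may differ. Poor embryo quality, one of the reasons given in 2.f, is close to what Aim 3 measures. Read literally, 2.f also removes from Aim 3 the couples who had a retrieval but no transfer because their embryos were poor, which selects on that aim's own outcome.

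If losses differ by arm, the groups compared are no longer the groups randomised. More non-transfer without antibiotics would favour non-inferiority once those couples are removed, and more with antibiotics would work against it. The exclusion is also unnecessary for the primary outcome: a couple with no transfer has a known result, which is no clinical pregnancy from that cycle.

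**Working it through.** **1. The plan's own sample size.** Inputs from F1: rate 0.41 in both arms, margin 0.15, z-values 1.96 and 0.8416.

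n per arm = (1.96 + 0.8416)² × 2 × 0.41 × 0.59 / 0.15² = 168.8, so 169. Then 169 / 0.95 = 177.9, so 178 per arm and 356 in total. This matches F1. The 5% allowance means that the calculation rests on 169 evaluable couples per arm.

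**2. Does power require the exclusion?** Chance of declaring non-inferiority = Φ((pE − pC + 0.15)/SE − 1.96), with SE = √(pC(1−pC)/nC + pE(1−pE)/nE). C is the antibiotic arm and E the no-antibiotic arm. At 41% in both arms this gives 80.1% with 169 per arm and 82.0% with 178. Power does not require it.

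**3. False declaration after exclusion.** Assumptions: 41% is per transfer in the antibiotic arm; the true deficit among all 178 randomised per arm is exactly 15 points; loss rates by arm are illustrative, because the document gives none. Then:

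- all-randomised pC = 0.41 × (1 − lossC), and all-randomised pE = that − 0.15
- per-transfer pE = all-randomised pE / (1 − lossE)
- n in each arm = 178 × (1 − loss)

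| Loss with vs without antibiotics | All randomised, C vs E | Per transfer, C vs E | n, C / E | SE | Declared non-inferior after exclusion |
|---|---|---|---|---|---|
| 5% vs 5% | 38.95% vs 23.95% | 41% vs 25.21% | 169.1 / 169.1 | 0.0505 | 1.7% |
| 4% vs 6% | 39.36% vs 24.36% | 41% vs 25.91% | 170.9 / 167.3 | 0.0506 | 2.4% |
| 2.5% vs 7.5% | 39.975% vs 24.975% | 41% vs 27.00% | 173.6 / 164.7 | 0.0509 | 3.9% |

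Last row: (0.2700 − 0.41 + 0.15)/0.0509 = 0.196, and Φ(0.196 − 1.96) = 3.9%. Simulation with 1,000,000 trials per case gives 1.7%, 2.4% and 3.8%. With the imbalance reversed, the closed form gives 1.2% (6% vs 4%) and 0.7% (7.5% vs 2.5%). The nominal rate is 2.5%.

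**4. How often the choice of set changes the result.** In 1,000,000 simulated trials with 41% per transfer in both arms and 5% loss in each (binomial transfer, then binomial pregnancy, 95% Wald interval in each set), the all-randomised and transfer-only sets reach opposite conclusions in about 4.4% of trials.

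**5. The all-randomised set is not always the stricter one.** Counting no-transfer couples as not pregnant shrinks an absolute difference. With 5% no-transfer in both arms, 15 points per transfer becomes 15 × 0.95 = 14.25 points per randomised couple.

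**The case against.** The strongest reply is that 2.f and 2.h were meant as the rule for a per-protocol or evaluable set. Several things fit this. The 5% is built into N, couples not intending transfer are ineligible, and the hypothesis in C1 concerns withholding antibiotics before embryo transfer. That reading is plausible, and a reader should not infer that the sponsor intends to abandon ITT. But the wording is unqualified, F4 defines no sets, and the unstated denominator of the 41% means that the sample size cannot settle the matter. The contradiction stands.

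A reader might also infer that the exclusions will bias the trial towards non-inferiority. The document does not support that. Embryologists who assess embryo outcomes are blinded (2.d), equivalent embryo development is hypothesised (Aim 3), and no loss rates by arm are given. Differential loss is possible but not indicated. At equal 5% loss, exclusion makes a false declaration against the all-randomised margin less likely (1.7%), and at 4% versus 6% it remains below nominal. Only the assumed threefold imbalance exceeds 2.5%.

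**Conclusion.** The point holds as a contradiction in the definition of the analysis set. The ITT analysis in F4 and the exclusions in 2.f and 2.h cannot all be followed, and the set that decides non-inferiority is not named. It must be settled before outcome data are seen, because the two candidate sets can disagree and neither is always the stricter.

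The size is modest: false declaration of 1.7% to about 3.9% over the cases with equal loss or higher loss without antibiotics, and clearly above nominal only when loss is much higher without antibiotics. These figures assume 41% per transfer and illustrative loss rates. It does not follow that N is wrong, since 356 reproduces exactly, or that the result is already biased in a known direction.

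**What to change.** **Replace 2.f and 2.h with wording such as:**

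> The ITT set is all randomised couples in the arm assigned. Couples with no retrieval or no transfer count as no clinical pregnancy from that cycle. Withdrawn couples stay in this set using routinely tracked outcomes unless they withdraw consent for data use. Exclusion for no transfer or withdrawal applies only to the per-transfer and per-protocol sets. Numbers and reasons are reported by arm.

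Aim 3 should likewise keep couples who had a retrieval but no transfer.

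**Add to F4 and F5:**

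- State which set decides non-inferiority, and report the other alongside it because of the shrinkage shown in step 5.
- State whether 41% is per cycle started or per transfer.
- For couples whose data cannot be used, include the sensitivity case that stresses non-inferiority: antibiotic-arm unknowns counted as pregnant, no-antibiotic-arm unknowns as not pregnant. Treating unknowns alike in both arms is not enough, because with similar missingness it pulls the difference towards zero.
- Define per-protocol adherence for both arms, and record antibiotic use in the no-antibiotic arm, which the verbal confirmation in 3.e does not clearly capture.

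**Optional, not part of the required fix:** require both sets to meet the margin. Compared with the all-randomised analysis alone, this costs about 1.2 points of power at 4% versus 6% loss and under 0.5 points at 2.5% versus 7.5%. At 5% versus 5%, power is 79.2%, against 80.2% for the transfer set alone and 82.7% for all randomised couples alone.

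**Cost of the required fix:** protocol and SAP wording, plus one adherence question in the no-antibiotic arm. It needs no extra visits and no change to the sample size.
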